8.6. Data Management

All information outlined in Section 8.3 will be recorded prospectively directly into an eCRF or retrospectively from medical records, if applicable, into the study database.

Data collection will be completed in a suitable electronic data capture (EDC) platform (Veeva EDC). All data collected will be stored at secure servers ensuring compliance with local or national regulations. Database lock is anticipated on the date the study is closed, i.e., when all documents and data have been collected, and reviewed and necessary data changes have been made after the last visit for the last subject. Additional details regarding data collection and validation procedures will be detailed in a data management plan.

The investigator is responsible for ensuring data is entered in a timely manner and verifying that data are accurate and correct. When the study is completed, the investigators must retain essential documents, e.g., source data that support information entered in the eCRF, for as long as needed to comply with regulatory guidelines and Sponsor requirements. The investigator must permit study-related monitoring, audits, institutional review board (IRB) review, and regulatory agency inspections and provide direct access to source data documents. The investigator will notify the Sponsor prior to moving or destroying any of the study documents. No records may be destroyed during the retention period without the written approval of the sponsor. No records may be transferred to another location or party without written notification to the sponsor.

8.7. Data Analysis

A detailed statistical analysis plan (SAP) will be prepared before the start of data collection. The SAP will detail the most appropriate statistical methodology and analyses to be performed in accordance with the study design and objectives. The SAP will provide further information to that discussed below (e.g., on handling of missing data). All analyses will be performed using SAS Version 9.4 or later.

Details of interim analyses will be described in the SAP.

8.7.1. Analysis Populations

8.7.1.1. Enrolled Population (EP)

The EP will consist of all patients for whom written informed consent has been obtained. This population will be used for disposition summaries.

8.7.1.2. Safety Population (SP)

The SP will include all patients in the EP who received at least one dose of belantamab mafodotin. The SP will be used for descriptive, safety and effectiveness analyses.

8.7.2. Statistical Methods

8.7.2.1. Descriptive Analysis

Continuous variables will be described (distribution) by their mean, standard deviation, median, Q1, Q3, extreme values (minimum and maximum) and the number of non-missing and missing data. Categorical variables will be described using frequency counts and percentages.

8.7.2.2. Analysis of Primary Objective

The primary objective for the study is to characterize RRMM patients treated with belantamab mafodotin. The following data on demographics, disease status, clinical characteristics and treatment history collected before or at the time of the first dose will be summarized for the SP (overall and by line of treatment):

- Age (years)
- Sex
- Body mass index (BMI) (kg/m²; derived from weight and height)
- ECOG performance status at index date
- Time from initial MM diagnosis to index date (months)
- Details of initial MM diagnosis (ISS stage, subtype, cytogenetic risk)
- Number of previous regimens by drug (combination) and class
- Refractory status (triple refractory, quad refractory, penta refractory)
- Progression status on last line of therapy
- Comorbidities during the baseline period
- Ocular health (Snellen visual acuity, slit lamp examination results) before/at index date
- Concomitant medications to belantamab mafodotin
- Laboratory measurements (i.e. lactate dehydrogenase, serum creatinine, creatinine clearance)

8.7.2.3. Analysis of Key Secondary Objectives

For the key secondary objectives, the following will be described for the SP (overall and by line of treatment) during active treatment exposure periods:

- Average cycle dose (sum of all doses divided by total number of administrations per patient)
- Frequency and timing of ophthalmic monitoring relative to belantamab mafodotin administration for each cycle (type(s), number of examinations; overall and according to monitoring before and after the occurrence of ocular AESIs as well as treatment dose and frequency)
- Ocular AESIs in RRMM patients exposed to belantamab mafodotin occurring during the study period:
 - Number, proportions, co-occurrence and time to (specific) ocular AESIs; overall and by System Organ Class (SOC) and Preferred Term (PT) terms (MedDRA classification) and according to severity, grade, seriousness, action taken, duration, impact on daily living and relationship to treatment as well as treatment dose and frequency
 - Number, proportion, severity, grade, seriousness and duration of ocular AESIs by ophthalmic monitoring frequency, type(s) and timing relative to administration
 - Severity, grade, seriousness and duration of ocular AESIs by their treatment impact (e.g., dose changes, duration of interruptions/delays, discontinuation), use of artificial tears and dry eye comorbidity

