3.9. Data analysis

Analysis populations:

Two analysis populations will be defined:

- Enrolled Population (EP) - All patients for whom written informed consent has been obtained
- Safety Population (SP) - All patients in the EP who received at least one dose of belantamab mafodotin. The SP will be used for descriptive, safety and effectiveness analyses

Statistical Methods:

For the primary objective, characteristics of RRMM patients treated with belantamab mafodotin per routine clinical care will be described for the SP (overall and by line of treatment). Characteristics to be described include demographics, disease status, clinical characteristics and treatment history collected before or at the time of the first dose.

For the secondary objectives, the following will be described for the SP (overall and by line of treatment):

- Treatment dose, duration, persistence and adherence
- Ocular AESIs during the study period:
- Number, proportions, co-occurrence, time to (specific) ocular AESIs and incidence rate (at the patient and event level); overall and by System Organ Class (SOC) and Preferred Term (PT) terms (Medical Dictionary for Regulatory Activities [MedDRA] classification) and according to severity, grade, seriousness, action taken, duration, impact on daily living and relationship to treatment as well as treatment dose and frequency

- Number, proportion, severity, grade, seriousness and duration of ocular AESIs by ophthalmic monitoring frequency, type(s) and timing relative to administration
- Severity, grade, seriousness and duration of ocular AESIs by their treatment impact (e.g., dose changes, duration of interruptions/delays, discontinuation), use of artificial tears and dry eye comorbidity
- Number and proportions of patients with dose reductions, interruptions/delays or discontinuing treatment due to an ocular AESI during the study period: overall and by comorbidity. This will include the description of the timing and dose of treatment re-introductions and the duration of dose reductions and interruptions/delays
- Treatment response (e.g., complete response [CR], very good partial response [VGPR]; partial response [PR]; according to IMWG criteria if feasible or to local standard practice) and time to events (i.e., death, progression, discontinuation)

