8. RESEARCH METHODS

8.1. Study Design

[figure not shown]
This multinational, multisite, non-interventional study will collect real-world data on the use, safety and effectiveness of belantamab mafodotin. Data will be analysed from approximately 150 RRMM patients from sites in selected countries across Europe.

Eligible RRMM patients from EU sites who are due to receive belantamab mafodotin will be consecutively invited for study enrolment by haematologists and/or oncologists affiliated with investigator sites participating in this study. In the event the enrolment rate after study start is too low to meet the expected 150 RRMM patients within the planned enrolment timeframe, eligible RRMM patients from sites who received their first belantamab mafodotin dose before study enrolment will be invited for study participation. As the study is non-interventional, the decision to treat patients with belantamab mafodotin will be made prior to and independent from the decision to enrol patients into the study, and baseline and follow-up assessments will be in accordance with local standard medical care. Investigators must refer to the SmPC (for European patients) for information on contraindications, warnings and precautions as well as use in specific populations.

Written informed consent will be obtained from all patients before enrolment into the study. Written informed consent may be obtained from family members of deceased patients, if allowed according to the regulatory and legal country-specific requirements of the participating site.

After obtaining informed consent, data will be collected retrospectively from medical records and prospectively, where applicable, from the time of the first dose of belantamab mafodotin to the end of follow-up at 15 months, study discontinuation for any reason, informed consent withdrawal or death, whichever comes first. The Investigator will follow ocular AESIs until resolved or until the last study visit of the patient.

[Figure 1](#) shows the patient and data flow in this study. For patients who will receive a first dose of belantamab mafodotin at or after study enrolment, baseline and outcome data will be entered into the electronic case report form (eCRF).

Figure 1 Patient and data flow

Abbreviations: eCRF=electronic case report form; Tx=treatment.

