	
 • Treatment discontinuation • Change in ophthalmic monitoring • Withdrawn from study • No action taken 	
Documented relationship to belantamab mafodotin	Categorical variable: 
 • Yes • No • Unknown 	Index date and post-index period
Ocular AESI outcome	Categorical variable: 
 • Fatal • Not recovered/not resolved • Recovered/resolved • Resolved with sequelae • Recovering/resolving • Unknown 	Index date and post-index period Please refer to Section 10
Ocular AESI stop date, if applicable	Date of ocular AESI resolution	Post-index period

Abbreviations: AESI=adverse event of special interest; KVA=Keratopathy and Visual Acuity; NCI CTCAE=National Cancer Institute Common Terminology Criteria for Adverse Events.
*MedDRA will be used for coding AEs. **Based on eye examination, characterised as corneal epithelium changes with or without symptoms. #Includes diplopia, vision blurred, visual acuity reduced and visual impairment. ##Includes dry eye, ocular discomfort, and eye pruritus @The WHO Drug Dictionary for medications will be used for coding drugs.

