8.3.7. Timings of Assessment

Data will be collected from patients' visits per routine clinical care either prospectively, directly into the eCRF or retrospectively from data already available in medical records into the eCRF (Table 7).

Table 7 Data Collection Plan

Variables	Baseline period	Standard of Care Visits*
Informed Consent	X	
Patient Eligibility	X	
Subject Characteristics	X	
Medical/Treatment History	X	
Concomitant Medications	X	X
Belantamab Mafodotin Treatment	X	X
Ophthalmic Monitoring and Results**	X	X
Ocular AESIs#	X	X
Effectiveness Evaluations		X

Abbreviations: AESI=adverse event of special interest.

*Data will be collected only if reported as part of standard of care visits, which are assumed to take place about every three weeks during treatment in accordance with local treatment guidelines until the end of follow-up. ** In the EU, eye examinations are required before the first three treatment cycles. Additional eye examinations are required promptly as clinically indicated (e.g., on worsening of ocular symptoms (BLNREP SmPC, 2021). #Other AEs and serious adverse events (SAEs) will not be actively solicited and based on spontaneous reporting.

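### Ocular AESIs are tabulated by monitoring frequency and by dose without a cut at AESI onset, so the groupings partly reflect the AESI itself

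*Protocol*

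**What the plan says.** Section 8.7.2.3 lists, among the key secondary analyses, "Number, proportion, severity, grade, seriousness and duration of ocular AESIs by ophthalmic monitoring frequency, type(s) and timing relative to administration". Section 3.9 repeats it. The bullet above it in both sections also breaks AESIs down by treatment dose and frequency. The only period in the lead-in to 8.7.2.3 is that items "will be described for the SP (overall and by line of treatment) during active treatment exposure periods", which covers time before and after an AESI.

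A before/after split does appear in 8.7.2.3: "overall and according to monitoring before and after the occurrence of ocular AESIs as well as treatment dose and frequency". It belongs to the bullet that describes monitoring and is not carried into the AESI bullets. Section 3.9 has no such split. Section 8.7.2.3 also defines average cycle dose over all of a patient's administrations.

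Elsewhere the protocol treats monitoring and dosing as responses to an AESI:
- Table 7 footnote (8.3.7): "Additional eye examinations are required promptly as clinically indicated", with worsening ocular symptoms as the example.
- Table 5 (8.3.5), under action taken: "Change in ophthalmic monitoring", alongside dose decrease, interruption/delay and discontinuation.
- Section 8.1: "The Investigator will follow ocular AESIs until resolved or until the last study visit of the patient".

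**The concern.** The grouping variables are measured after baseline and are partly produced by the outcome being tabulated. A patient with an AESI tends to be examined more, and may have the dose lowered or delayed, because of it. A long AESI also has more time to accumulate examinations. Time on treatment adds to this: monitoring is recorded only until discontinuation (8.3.4), so a longer-treated patient has both more examinations and more opportunity for an AESI.

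A table of AESI proportion by monitoring frequency invites reading across its columns, and Section 7 says the results will inform clinical practice. If the groups are formed from the whole treatment period, any gradient may be only the protocol's own response rules and time on treatment.

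**Working it through.** The protocol gives no figure for these tables, so there is nothing to reproduce. The checks set the true effect to zero and ask what the tables would show.

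**1. Monitoring frequency (simulation)**

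Inputs from the protocol:
- 71% with an AESI (keratopathy in the pivotal study, Section 6.1, as a stand-in for any ocular AESI).
- 21-day cycles (8.3.1) and N = 150 (8.5).
- Examinations concentrated in the first four cycles (6.1).
- 3% discontinuing for ocular reactions (6.1).

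Assumptions:
- Median treatment 2.8 months (pivotal PFS as proxy) or 6 months.
- Examination probability about 0.85 per cycle in cycles 1–4 and about 0.3 later.
- 0, 0.25, 0.5 or 1 extra examinations per cycle after onset.
- Constant AESI hazard, with no effect of monitoring on occurrence or detection.

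Patients were split at the median. Entries are the percentage with an AESI, low / high group (200,000 patients). A rerun with another seed agreed to within one point.

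| Extra exams per cycle after AESI | Count, 2.8 mo | Count, 6 mo | Per-cycle rate, 2.8 mo | Per-cycle rate, 6 mo |
|---|---|---|---|---|
| 0 | 54 / 91 | 58 / 93 | 84 / 57 | 85 / 57 |
| 0.25 | 53 / 97 | 51 / 97 | 80 / 62 | 77 / 64 |
| 0.5 | 47 / 97 | 47 / 98 | 61 / 100 | 71 / 71 |
| 1 | 44 / 99 | 45 / 99 | 42 / 100 | 45 / 100 |

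By count, the high group exceeded the low group in about 100% of 1,000 replicates at N = 150. With no triggered examinations the gap is already 91 − 54 = 37 points at 2.8 months, from time on treatment alone. One triggered examination per cycle widens it to 99 − 44 = 55. With 30% discontinuing after an AESI, the count split still gave 50–61% versus 87–97%.

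By rate, the direction is reversed in four of the eight scenarios, absent in one and positive in three. Front-loaded examinations give short-treated patients high rates, while triggered examinations raise the rates of AESI patients.

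**2. Average dose (arithmetic)**

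Let p = 0.71 have an AESI and let a share r of them have the dose reduced because of it. If nobody else is reduced, the reduced group is 100% AESI. The full-dose group has p(1 − r) / (1 − pr):
- r = 0.25: 0.5325 / 0.8225 = 65%
- r = 0.50: 0.355 / 0.645 = 55%
- r = 0.75: 0.1775 / 0.4675 = 38%

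If one in ten AESI-free patients is also reduced, r = 0.50 gives 0.355 / (0.355 + 0.029) = 92% in the reduced group and 0.355 / (0.355 + 0.261) = 58% in the full-dose group. The values of r and the one in ten are assumptions.

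**3. Does a pre-onset grouping remove it?**

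In the same simulation, patients on treatment and AESI-free after cycle 2 were grouped by examinations in cycles 1–2. Later AESIs were 70–71% versus 71% in all 24 scenarios (two treatment durations, three discontinuation rates, four levels of extra examinations).

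**4. What it does not remove**

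Table 5 identifies keratopathy by eye examination. Suppose onset is h = 0.20 per cycle, symptoms reveal s = 0.75 of cases each cycle, and a pre-dose examination reveals any remaining case. Among patients with no AESI found in cycle 1, the undetected share is L = h(1 − s) / (1 − hs) = 0.05 / 0.85 = 0.059. An examination before dose 2 removes these patients from the AESI-free group; without one they stay. AESIs then found by symptoms in cycle 2:
- examined: hs = 0.15, or 15%
- unexamined: s[L + (1 − L)h] = 0.75 × (0.059 + 0.188) = 0.185, or 19%

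The gap disappears only at s = 1. Examination would look mildly protective with no real effect.

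**The case against.** The best reply is that this is a descriptive study. No hypotheses are tested (Section 7), the ENCePP checklist says no comparative analyses are planned, and the methodological detail is left to a SAP that is not shown. The monitoring objective is stated per cycle. Dosing after an AESI is already described as a consequence in 8.7.2.3 and 8.7.2.4, and monitoring is already described before and after AESIs.

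Much of this stands, and it rules out three stronger readings that a reader might infer:
- That the table is bound to show more AESIs with more monitoring. This follows under an examination count. On a per-cycle rate the direction can vanish or reverse. Nor is triggered monitoring the only cause: time on treatment produces much of the count gap.
- That the protocol prescribes a whole-period grouping. It does so for average cycle dose. For monitoring frequency, and for the use of average dose as the grouping, it is the plain reading of bullets without a window.
- That the study sets out to test whether monitoring works as risk minimisation. No section says so; the risk-minimisation measures named are educational materials.

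Descriptive status does not settle the matter. The protocol itself fixes these cross-tabulations in two sections and applies the before/after distinction only to the neighbouring monitoring bullet.

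**Conclusion.** The point holds in limited form. On the plain reading of 3.9 and 8.7.2.3, the AESI tables by monitoring and by dose use groupings that an AESI can change, and cannot be read as AESI occurrence by monitoring or dosing. With zero true effect, a count grouping gives a contrast of roughly 35 to 55 percentage points, a per-cycle rate can point either way, and a whole-period average dose moves AESI-driven reductions into the low-dose group. These sizes rest on assumed examination, reduction and time-on-treatment rates, which the protocol does not give. AESI duration by monitoring frequency has the same weakness by reasoning but was not quantified. The primary objective and the overall AESI incidence are unaffected. The change should be made before the tables are programmed.

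**What to change.** In 3.9 and 8.7.2.3, add for the tables of AESI occurrence and severity:
- Dose and dosing interval are those in force before AESI onset.
- Monitoring frequency, type and timing come only from examinations before onset, either cycle by cycle or at a fixed landmark, among patients on treatment and AESI-free at that point.
- Monitoring and dosing after onset are shown only as consequences of the AESI, as the existing treatment-impact and before/after bullets already do.

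The monitoring table should carry a note that keratopathy is found by examination, that unexamined cycles can therefore show more later AESIs, and that the table does not estimate an effect of monitoring.

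The cost is wording and programming. Administration, examination and onset dates are already collected (Tables 3 to 5). The downsides are smaller cells at N = 150 and the residual detection bias described above.

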8.7.2.4. Analysis of Other Secondary Objectives

In addition, the following will be described for the SP (overall and by line of treatment):

- Exposure-adjusted incidence rate with 95% CI, overall and by SOC and PT names
 - Defined as the number of patients with at least one (specific) AE during follow-up divided by the sum of person-months at risk in the study.
 - Person-months at risk is defined as the duration of follow-up for patients without AEs plus the duration of follow-up until the date of the first (specific) AE for patients with an AE.
- Exposure-adjusted event rate with 95% CI, overall and by SOC and PT names
 - Defined as the number of (specific) AESIs during follow-up divided by the sum of person-months at risk in the study.
 - Person-months at risk is defined as the duration of follow-up.
- For patients with dose reductions, interruptions/delays or discontinuation of belantamab mafodotin treatment **due to an ocular AESI** during the study period, the following will be summarized (overall and by comorbidity, ocular AESI type and ocular AESI severity as well as treatment dose and frequency):
 - Number and proportions of patients
 - Primary reasons for dose reductions, interruptions/delays or discontinuation of treatment due to any AE
 - Belantamab mafodotin treatment patterns after occurrence of an ocular AESI (i.e., order of treatment changes and timing)

- Median, 95% CIs and 25th and 75th percentiles using the Kaplan-Meier (KM) method for time to dose reductions, interruptions/delays or discontinuation
- Duration of dose reductions and interruptions/delays or discontinuations
- Belantamab mafodotin treatment adherence, i.e., the total duration of treatment in days divided by the total follow-up time in days.
- Belantamab mafodotin treatment persistence, i.e., the proportion of patients still on treatment at specified time points, including 3-, 6-, 12- and 15-months of follow-up
- Treatment response (e.g., sCR, CR, VGPR or PR):
 - Best treatment response during follow-up
 - Treatment response at specified time points, including 12- and 15-months of follow-up
 - Proportion of patients with a maintained response (PR or better) at specific time points, including 12- and 15-months of follow-up
 - ORR with 95% CIs calculated based on the exact binomial distribution (Clopper-Pearson method)
- Median, 95% CIs and 25th and 75th percentiles using the KM method for:
 - OS (overall and based on response / non-response to treatment)
 - rwPFS (overall and based on response / non-response to treatment)
 - DoR
 - DoT
- OS rates with 95% CIs at specified time points, including 12- and 15-months of follow-up

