As shown in [Figure 1](#), eligible RRMM patients from sites who received their first belantamab mafodotin dose before study enrolment will only be invited for study participation if this is deemed necessary based on the enrolment rate in the EU.

Belantamab mafodotin use and ophthalmic monitoring data will be collected while patients are on treatment. Safety and effectiveness data will be collected regardless of whether patients are on treatment or have discontinued treatment during follow-up.

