8.2.3. EU Setting Considerations

8.3. Variables

8.3.1. Definitions

[figure not shown]
The following definitions apply to the different timings of data collection (see [Figure 2](#)):

- **Index date** is defined as the time of the first (non-missing) dose of belantamab mafodotin.
- **The baseline period** for data collection is defined as the time from the initial MM diagnosis until the index date (the first dose of belantamab mafodotin).
- **The post-index period** spans from the index date until the end of follow-up at 15 months, study discontinuation for any reason, informed consent withdrawal or death; whichever comes first.
- **The post-index treatment period** is defined as the duration of the belantamab mafodotin line of treatment (DoT). This spans from the index date until the confirmed decision date of permanent discontinuation of belantamab mafodotin treatment, the

confirmed date of a new line of treatment or the date of the end of follow-up at 15 months, study discontinuation for any reason, informed consent withdrawal or death; whichever comes first.

- **The study period** spans from the time from the initial MM diagnosis until the end of follow-up at 15 months, study discontinuation for any reason, informed consent withdrawal or death; whichever comes first.
- **Active treatment exposure periods** are defined as the time that belantamab mafodotin is considered to have a treatment effect during the post-index treatment period. This period includes all doses occurring within 70 days of the previous dose (belantamab mafodotin's half-life) from the date of the first belantamab mafodotin dose of that sequence to the date of the last dose +70 days or the date of the end of the post-index treatment period; whichever comes first.

Figure 2 Timings of Data Collection

[figure not shown]
Abbreviations: MM=multiple myeloma.

The following definitions apply to collection of treatment data:

- **Line of treatment** is defined as one or more completed cycles of a single agent, a regimen consisting of a combination of several drugs, or a planned sequential therapy of various regimens (Rajkumar, 2015).
- **A treatment cycle** is defined as the belantamab mafodotin label-approved dosing interval, which is 21 days (with a real-world scheduling grace period of +7 days).
- **Treatment discontinuation** is defined as a recorded clinician decision (with an associated decision date) to permanently discontinue belantamab mafodotin treatment.

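### The ocular AESI rates called exposure-adjusted divide by all follow-up time, on or off drug, and Section 8.7.2.3 gives two conflicting windows for counting AESIs

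*Protocol*

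**What the plan says.** **Rates (Section 8.7.2.4).** The heading for the second rate is "Exposure-adjusted event rate with 95% CI, overall and by SOC and PT names". It is "Defined as the number of (specific) AESIs during follow-up divided by the sum of person-months at risk in the study", and "Person-months at risk is defined as the duration of follow-up". For the incidence rate, "Person-months at risk is defined as the duration of follow-up for patients without AEs plus the duration of follow-up until the date of the first" event in patients who have one. Neither definition refers to dosing. Section 3.9 repeats the exposure-adjusted label.

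**What follow-up contains (Section 8.1).** "Safety and effectiveness data will be collected regardless of whether patients are on treatment or have discontinued treatment during follow-up". In contrast, "Belantamab mafodotin use and ophthalmic monitoring data will be collected while patients are on treatment"; Section 8.3.4 likewise stops the monitoring data at permanent discontinuation. A footnote to Table 5 bases keratopathy on eye examination.

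**Key secondary window (Section 8.7.2.3).** The lead sentence sets the description "overall and by line of treatment) during active treatment exposure periods". Section 8.3.1 ends such a period at "the last dose +70 days or the date of the end of the post-index treatment period; whichever comes first". The post-index treatment period itself ends at the earliest of the confirmed discontinuation decision, a new line of treatment, end of follow-up, study discontinuation, consent withdrawal and death. The AESI bullet under the same lead sentence instead counts events over the study period, which Section 8.3.1 starts at the initial myeloma diagnosis.

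**The concern.** An exposure-adjusted rate is read as events per unit of time under the drug's influence. Section 8.3.1 defines that time, but the rates do not use it. If patients typically stop treatment well before month 15, much of the denominator is off-drug time. In that time the examination data that reveal keratopathy are no longer gathered; keratopathy was the most frequent adverse reaction in the cited pivotal study, at 71%. Section 8.9.1 plans to compare the safety results with trials and published real-world studies, and Section 7 uses them for the risk-benefit profile. A follow-up rate read as an exposure rate could understate on-drug ocular toxicity there. Subgroups that stop early contribute relatively more off-drug time, so rates by subgroup may differ for that reason alone.

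The conflict in Section 8.7.2.3 is a second problem. Two programmers following the text could report different AESI counts. Under the narrower reading, the 70 days in which Section 8.3.1 treats the drug as still active are cut short for patients who stop.

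**Working it through.** The protocol states no AESI rate or person-time total, so there is no figure to reproduce. The size can only be illustrated.

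**Inputs.** From Section 6.1: median PFS 2.8 months (95% CI 1.6 to 3.6), median OS 13.7 months (lower limit 9.9), and OS of about 7 to 10 months in the cited literature. From Section 8.3.1: a 70-day tail and a 21-day cycle. Follow-up is capped at 15 months. **Assumptions:** PFS stands in for time from first dose to the discontinuation decision; that time and OS are independent and exponential; there is no other loss to follow-up; a month is 30.4375 days.

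**Hazards.** λo = ln 2/13.7 = 0.0506; λx = ln 2/2.8 = 0.2476; s = λo + λx = 0.2981 per month.

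**Mean months per patient**
- Follow-up: F = (1 − e^(−15λo))/λo = (1 − 0.4682)/0.0506 = 10.5.
- To the decision: T = (1 − e^(−15s))/s = (1 − 0.0114)/0.2981 = 3.3.
- To a window end δ months after the decision: W = (1 − e^(−λoδ))/λo + e^(λxδ) × (e^(−sδ) − e^(−15s))/s.
 - Decision on the day of the last dose, δ = 70/30.4375 = 2.30: W = 2.17 + 1.767 × 1.651 = 5.09.
 - Decision 21 days after the last dose, δ = 49/30.4375 = 1.61: W = 1.55 + 1.490 × 2.037 = 4.58.

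**Person-time ratio.** F/W = 10.51/5.09 = 2.1, or 10.51/4.58 = 2.3. With the 21-day gap, 1 − 4.58/10.51 = 56% of follow-up lies beyond last dose plus 70 days. F/W by scenario, 21-day gap (the 6.0-month row is an added assumption):

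| Median time on drug (months) | OS 7 | OS 9.9 | OS 13.7 |
|---|---|---|---|
| 1.6 | 2.53 | 2.82 | 3.05 |
| 2.8 | 1.99 | 2.16 | 2.29 |
| 3.6 | 1.79 | 1.92 | 2.03 |
| 6.0 | 1.49 | 1.56 | 1.62 |

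**From person-time to rates.** With hazard h inside the window and r outside it, the Section 8.7.2.4 event rate is [hW + r(F − W)]/F. The dilution factor is therefore F/[W + (r/h)(F − W)]. With W = 4.58 and F − W = 5.93:
- r = 0: 10.51/4.58 = 2.3
- r = 0.1h: 10.51/5.17 = 2.0
- r = 0.5h: 10.51/7.55 = 1.4
- r = h: 1.0

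The incidence rate stops each patient's time at the first event, so it is diluted less. Simulated at h = 0.30 per month, it is 0.154 against 0.30 when r = 0 (factor 1.95) and 0.251 against 0.30 when r = 0.5h (factor 1.2).

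**The tail cut in Section 8.7.2.3.** If the decision comes 21 days after the last dose, 70 − 21 = 49 of the 70 tail days fall outside the window. The share of window person-time removed is (4.58 − 3.32)/4.58 = 28% (15% to 40% across the scenarios), and the same share of events under a constant hazard. At h = 0.30, the proportion of patients with any AESI in the window falls from about 65% to about 50%.

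**The case against.** - **The rates are internally coherent.** Events during follow-up are divided by time in follow-up, in line with collecting safety data on and off treatment. A reader might infer a mismatch between numerator and denominator; the text does not support that. The fault is the label and the missing exposure-based rate.
- **Late events are not discarded.** Section 8.3.5 records AESIs during and after administration to the end of follow-up, and Section 8.7.2.4 counts them. They could be lost only from the Section 8.7.2.3 description, and only if its lead sentence overrides its bullet. Section 3.9 lists the same summaries over the study period with no exposure restriction, which favours the wider reading.
- **A halved rate is not established.** The ratio of about 2 is a ratio of person-time. It becomes a ratio of rates only if no AESI starts outside the window, and the protocol gives no off-drug hazard.
- **These are other secondary measures** in a descriptive study without hypotheses. The documents do not make them the main safety result.

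All four points stand. They limit the size and reach of the problem, but they do not make follow-up time exposure time or reconcile the two windows. The end of monitoring data collection also does not mean that eye examinations stop: AESIs found later are still reportable. Off-drug ascertainment of keratopathy is therefore likely to be weaker, not absent.

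**Conclusion.** The concern holds in this form. The two rates in Section 8.7.2.4 are follow-up rates presented as exposure-adjusted. Their person-time is about 2.1 to 2.3 times exposure time in the base case and about 1.5 to 3 times across scenarios. This rests on PFS as a proxy for time on drug, exponential times and an assumed gap of 0 or 21 days between last dose and decision (21 days in the scenarios). The effect on the event rate runs from that full factor down to none, depending on the unknown off-window hazard; the incidence rate is affected less. Section 8.7.2.3 independently contradicts itself on the AESI window. Its narrower reading removes the tail after the decision from the key secondary description only.

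**What to change.** 1. In Section 8.7.2.4, compute the exposure-adjusted incidence and event rates with events and person-time both taken from one analysis window: first dose to last dose plus 70 days, not cut at the discontinuation decision. State explicitly whether the start of a new line of treatment ends the window. Section 8.3.1 currently makes it a stop, and removing that silently would attribute events under later therapy to belantamab mafodotin exposure.
2. Keep the all-follow-up rates as a second measure and name them follow-up rates, in Section 3.9 as well.
3. In Section 8.7.2.3, state one post-index AESI window in place of the two, and report AESIs that start after it separately.

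The cost is wording and one extra table. Dose dates, AESI onset dates and follow-up dates are already collected. The reported exposure-adjusted rates will probably be higher than under the present definition.
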